2.3 Study endpoints

Main endpoints and definitions:

This study primarily evaluates the proportion of patients with YWHAB

high expression locally advanced rectal cancer who achieve tumor downstaging (ypTNM 0-I stage) after neoadjuvant therapy with mFOLFOX6 combined with Citrus Flavonoid Tablets (Aimianlang). The tumor downstaging rate (ypTNM 0-I stage) refers to the percentage of patients with locally advanced rectal cancer who, after receiving neoadjuvant chemotherapy with mFOLFOX6 or mFOLFOX6 + Citrus Flavonoid Tablets (Aimianlang), have their postoperative pathological stage of the surgical specimen classified as ypTNM 0-I stage.

Secondary endpoints and definitions:

- (1) The degree of pathological remission is defined as follows: ① Complete Remission (CR): All tumor target lesions have disappeared, no new lesions have appeared, and tumor markers are normal, lasting at least 4 weeks. ② Partial Response (PR): The sum of the maximum diameters of tumor target lesions has decreased by at least 30%, lasting at least 4 weeks. ③ Stable Disease (SD): The sum of the maximum diameters of tumor target lesions has not decreased by more than PR, or increased by less than PD. ④ Disease Progression (PD): The sum of the maximum diameters of tumor target lesions has increased by at least 20%, or new lesions have appeared.
- (2) The 3-year disease-free survival rate (DFS) is the proportion of patients who have not experienced any of the following events from the start of randomization to the end of year 3: disease progression, surgical gross/microscopic tumor residue, local recurrence, distant metastasis, or death for any reason, whichever occurs first.
- (3) Overall survival time (OS) is the time from randomization to death for any reason.
- (4) Tumor regression grading TRG: TRG 0 means no residual tumor cells, TRG 1 means a single cell or a small group of cells; TRG 2 means residual cancer with a proliferative response to connective tissue; TRG 3 means minimal evidence of tumor response.
- (5) Safety indicators, treatment-related adverse reaction rate (grade III and

above): Antitumor drugs/therapy In clinical trials, drug adverse reactions determined to be related to drug therapy at grade III and above, excluding nonspecific infusion reactions.

3. Selection and withdrawal of subjects

3.1 Inclusion criteria:

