4.1 Study treatment grouping

This study is a prospective, open-label, double-arm, Phase II clinical trial that includes a neoadjuvant treatment group using the mFOLFOX6 regimen and a neoadjuvant treatment group combining the mFOLFOX6 regimen with Citrus Flavonoid Tablets (Aimalang). The study aims to enroll patients with locally advanced rectal cancer who are in clinical stage I, II, or III. Endoscopic biopsy specimens will be collected for YWHAB immunohistochemical testing to identify patients with high YWHAB expression in locally advanced rectal cancer. These patients will then be randomly assigned to either the mFOLFOX6 treatment group or the mFOLFOX6 combined with Citrus Flavonoid Tablets (Aimalang) treatment group for neoadjuvant therapy. The mFOLFOX6 regimen involves 4-6 cycles before surgery and 6-8 cycles after surgery, with each cycle lasting 14 days: on day 1, 85 mg/m² of oxaliplatin is administered intravenously over 180 minutes; on day 1, 400 mg/m² of leucovorin is administered intravenously over 120 minutes; and on day 1, 2400 mg/m² of 5-fluorouracil is administered continuously intravenously for 46 hours. The Citrus Flavonoid Tablets (Aimalang) treatment regimen involves taking 500mg of Citrus Flavonoid Tablets (Aimalang) orally three times daily, with doses given on days 1-14 of each 14-day cycle.

This trial allows for dose adjustments. Patients who experience disease progression during neoadjuvant therapy may stop the study treatment and directly undergo surgery or follow local guidelines. If a patient cannot tolerate the planned 6 cycles of neoadjuvant therapy, early surgery can be considered. Any patient who has received another anticancer regimen before surgery will stop the study treatment and be managed according to local guidelines. The postoperative

treatment for both groups is determined by the investigator, which may include continuing the mFOLFOX6 regimen combined with Citrus Flavonoid Tablets (Aimalang). It is important to note that all patients in the control group are prohibited from taking Citrus Flavonoid Tablets (Aimalang) without authorization during the trial. If a patient needs to take this medication for any reason, they should consult their primary physician, who will decide whether to use an alternative or discontinue the patient's participation in the trial.

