- 12. Lead electrocardiogram: attention should be paid to QT, QTc and P-R intervals. If there are abnormalities, other relevant tests should be done according to the investigator's judgment;
- Document adverse events;
- Imaging evaluation: Imaging evaluation was performed after 6 cycles and 12 cycles of mFOLFOX6 regimen adjuvant chemotherapy, including chest, abdominal and pelvic enhanced CT and pelvic MRI. Any subject suspected of disease progression during treatment (e.g., symptom deterioration) could undergo unplanned imaging evaluation.

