5.3 End of treatment/exit from study visit

When the subject has completed the study treatment/exited the study, relevant assessments and examinations are required. They should be performed as follows:

- Weight and ECOG score;
- Life signs: pulse, respiratory rate, body temperature and blood pressure;
- Comprehensive physical examination: general condition, head and face, skin, lymph nodes, eyes, ear, nose and throat, oral cavity, respiratory system, cardiovascular system, abdomen, reproductive and urinary system, musculoskeletal, nervous system and mental state;
- Complete blood count: red blood cell count, hemoglobin, platelet count,

white blood cell count, neutrophil count and lymphocyte classification count;

- Routine urine: white blood cells, red blood cells, proteinuria; if proteinuria is greater than or equal to 2+, 24-hour urine protein quantification should be added;
- Blood biochemical: ALT, AST, γ -GT, TBIL, DBIL, AKP, BUN or urea (preferably BUN), TP, ALB, Cr, GLU, K+, Na+, Ca2+, Mg2+, Cl-;
- Tumor markers;
- Coagulation function: activated partial thromboplastin time (APTT), prothrombin time (PT), thrombin time (TT), fibrinogen (FIB), international normalized ratio (INR);
- 12. Lead electrocardiogram: attention should be paid to QT, QTc and P-R intervals. If there are abnormalities, other relevant tests should be done according to the investigator's judgment;
- Document adverse events.

5.4, follow-up period

The survival follow-up period ends when the subject dies, is lost to follow-up, withdraws from informed consent and refuses to continue providing information, or the sponsor terminates the study. During this period, a visit is conducted every three months through telephone or other effective methods to collect survival information and details about subsequent anti-tumor treatments (if the subject starts new anti-tumor treatment, the treatment plan and its duration should be recorded).

For subjects without imaging evidence of disease progression, imaging assessments should continue to be conducted at the frequency specified in this study until the subject experiences disease progression, death, loss to follow-up, withdrawal of informed consent and refusal to continue providing information, initiation of other anti-tumor treatments, or termination of the study by the sponsor. Every effort should be made to obtain imaging evidence of disease

progression in these subjects.

6. Effectiveness evaluation

6.1 Effectiveness parameters:

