The main efficacy indicator of this study was the proportion of patients in each treatment group who achieved tumor downstaging (ypTNM 0-I stage), and the secondary efficacy indicators were the proportion of patients with complete pathological remission, 3-year disease-free survival (DFS), overall survival time (OS) and tumor regression grade TRG.

6.2 Evaluation criteria of effectiveness:

This study evaluated the proportion of patients with YWHAB high expression locally advanced rectal cancer who achieved tumor downstaging (ypTNM 0-I stage) in neoadjuvant treatment with mFOLFOX6 combined with citrus flavonoid tablets (Aimalang).

- (1) Downstaging rate of tumor (ypTNM 0-I stage): the proportion of patients with locally advanced rectal cancer who received mFOLFOX6 or mFOLFOX6 combined with citrus flavonoid tablets (Aimalang) as neoadjuvant chemotherapy, and the proportion of patients with postoperative pathological stage of ypTNM 0-I stage in surgical specimens.
- (2) The degree of pathological remission is defined as follows: ① Complete Remission (CR): All tumor target lesions have disappeared, no new lesions have appeared, and tumor markers are normal, lasting at least 4 weeks. ② Partial Response (PR): The sum of the maximum diameters of tumor target lesions has decreased by at least 30%, lasting at least 4 weeks. ③ Stable Disease (SD): The sum of the maximum diameters of tumor target lesions has not decreased by more than PR, or increased by less than PD. ④ Disease Progression (PD): The sum of the maximum diameters of tumor target lesions has increased by at least 20%, or new lesions have appeared.

Subjects who did not meet the primary endpoint criteria are included in the denominator but not in the numerator.

- (3) When determining the disease-free survival (DFS), clinical deterioration without clear evidence of disease progression according to the RECIST 1.1 criteria is not considered a disease progression. For subjects who died without prior reported disease progression, it is considered that the disease progressed at the time of death. Subjects who have neither experienced disease progression nor died will be censored at their last evaluable tumor evaluation date. Independent central imaging review will be conducted to confirm the independent central imaging service provider of the subject, which will receive all images from the research center and assess the subject's disease progression according to the RECIST 1.1 criteria.

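### Follow-up imaging is required but has no stated interval, and the only scan times conflict with the regimen, so 3-year DFS depends on how each site scans

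*Combined protocol and SAP*

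**What the plan says.** - **Scan times during treatment (5.2).** "Imaging evaluation was performed after 6 cycles and 12 cycles of mFOLFOX6 regimen adjuvant chemotherapy". Extra scans are optional and tied to suspicion while on treatment: "Any subject suspected of disease progression during treatment (e.g., symptom deterioration) could undergo unplanned imaging evaluation".
- **Regimen (4.1).** 14-day cycles, "4-6 cycles before surgery and 6-8 cycles after surgery". The same section leaves postoperative treatment to the investigator.
- **End-of-treatment visit (5.3).** The list of assessments contains no imaging.
- **Follow-up (5.4).** For patients without imaging progression, "imaging assessments should continue to be conducted at the frequency specified in this study until the subject experiences disease progression", or until another listed stopping event. The section adds a best-effort clause on obtaining imaging evidence. The only contact with a stated interval is 3-monthly, by telephone or other means, to collect survival and later treatment. Section 6.2(4) has 3-monthly telephone contact on disease and survival.
- **DFS rules (2.3 and 6.2(3)).** The 3-year DFS rate runs "from the start of randomization to the end of year 3". Clinical deterioration without RECIST 1.1 evidence is not progression. Patients with neither progression nor death "will be censored at their last evaluable tumor evaluation date". Images go to independent central review.
- **Analysis (8.3).** Kaplan-Meier curves, a log-rank test and Cox hazard ratios.

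**The concern.** The censoring rule makes the date of the last scan part of the endpoint. A patient who is well at three years contributes three years of follow-up only if a scan was done at about that time. Section 5.4 sends the site to a frequency specified elsewhere, and what it finds is a pair of cycle numbers that have run out and that many patients could not reach under the protocol's own regimen. Two sites can therefore both comply while scanning at very different rates. Because no interval is stated, a missed follow-up scan cannot be identified as a deviation.

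At stake are the size of the 3-year DFS estimate, the comparability of the arms where treatment is known to those ordering scans, and the inputs to the log-rank test and the Cox model. Central review does not help, because it can read only images that were taken.

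**Working it through.** The documents give no expected DFS rate, event count or DFS power, so there is no figure of the plan's own to reproduce. The check has three parts.

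**1. Cycle anchors against the regimen (inputs: 4.1 and 5.2).**

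| Before surgery | 6 after | 7 after | 8 after |
|---|---|---|---|
| 4 | 10 | 11 | 12 |
| 5 | 11 | 12 | 13 |
| 6 | 12 | 13 | 14 |

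- If the cycles are counted as adjuvant, as written, the maximum is 8 and the second scan never falls due.
- If they are counted over the whole course, 4+6, 4+7 and 5+6 stop at 10 or 11 and miss the second scan. These are combinations, not proportions of patients; the documents do not say how often each will occur.

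**2. Where the last dated scan falls.** Cycle 12 ends after 12 x 14 = 168 days of treatment. Assume 8 to 16 weeks around surgery (not in the documents) and 30.4375 days per month:

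- (168 + 56) / 30.4375 = 7.4 months; (168 + 112) / 30.4375 = 9.2 months.
- Remaining to month 36: 36 - 9.2 = 26.8 to 36 - 7.4 = 28.6 months with no dated scan. This treats randomisation and treatment start as the same day.

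**3. What scanning practice does to the estimate.** Assumptions, none from the documents: true 3-year DFS 75%, exponential events, last dated scan at month 8.

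*Scenario A: later events are found when they occur, and a fraction q of the patients event-free at month 36 has an evaluation then. The rest are censored at month 8.*

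- S(8) = 0.75^(8/36) = 0.938. Events between months 8 and 36: 0.938 - 0.75 = 0.188.
- Just after month 8 the risk set is 0.188 + 0.75q, with no further censoring before month 36.
- Kaplan-Meier at month 36 = 0.938 x 0.75q / (0.188 + 0.75q).

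| q | Estimate | Error in points |
|---|---|---|
| 0.25 | 47% | -28 |
| 0.50 | 62% | -13 |
| 0.75 | 70% | -5 |
| 1 | 75% | 0 |

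If coverage is 75% in one arm and 50% in the other, two arms with identical DFS differ by 70.3 - 62.5 = about 8 points.

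*Scenario B: recurrence is found only at a scan. After month 8 there are scan opportunities every 6 months from month 14 to month 50, each attended with a fixed probability (simulation).*

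| Probability attended | Estimate | Error in points |
|---|---|---|
| 25% | about 83% | +8 |
| 50% | 80-81% | +5 to +6 |
| 75% | 78-79% | +3 to +4 |
| 100% | about 77% | +2 |

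The last row is still high because the final opportunity before month 36 is at month 32, and 0.75^(32/36) = 77%. Regular 3-monthly scans that include month 36 return 75%.

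**The case against.** The strongest reply is that the protocol does require imaging to go on. Section 5.4 keeps it running to progression or another stopping event and adds: "Every effort should be made to obtain imaging evidence of disease" progression. The telephone contacts are a separate paragraph and do not replace scans. This stands. A reader might infer that imaging ends at cycle 12, that 3-year DFS therefore cannot be answered, or that the estimate must be too low. The documents support none of these. Total loss of later scans would breach section 5.4, and scenario B shows that late detection pushes the estimate up.

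Second, the two anchors are six cycles apart, 6 x 14 = 84 days, so the intended frequency may be about every 12 weeks, close to the 3-monthly contacts. On that reading scans reach month 36 and DFS can be estimated. But the protocol does not say this, and the anchors do not produce a constant interval. With whole-course counting, a patient with 6 preoperative cycles has surgery between the two scans. On the gap assumed above they are then 84 + 56 = 140 to 84 + 112 = 196 days apart, against 84 days (without delays) when surgery comes before cycle 6.

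Third, the two cycle ranges mirror each other around 12 (4+8, 5+7, 6+6), so a total of 12 may have been meant. That is plausible but unstated, and it still conflicts with the word adjuvant in section 5.2.

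Fourth, DFS is secondary, has no power or event target, and the primary endpoint is pathological. This stands and limits the severity. Differential scanning by arm is a possibility that the open-label design leaves open; no text creates it.

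A reader might also infer that patients operated on after 4 or 5 cycles go to surgery unscanned. The background section on the significance of the study provides for preoperative assessments without saying whether they include imaging, so that is a matter to reconcile, not an established gap.

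**Conclusion.** The concern holds in this form: follow-up imaging is required at a frequency that is never given as an interval, and the only scan times contradict the regimen. Scan density, censoring dates and hence 3-year DFS are left to site practice. The direction of error is not fixed. Under the assumed 75% true DFS, the examples run from about 13 points low (half of event-free patients scanned at month 36, later events found promptly) to about 3 to 8 points high (irregular scans, late detection). These are illustrations that rest on the assumed rate, the month-8 scan and the coverage figures; they are not forecasts.

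Severity is moderate. The endpoint is secondary, but this is more than missing detail, because the stated schedule contradicts section 4.1 and scans not taken cannot be recovered at analysis.

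**What to change.** - Reconcile the scan times in section 5.2 with the cycle numbers in section 4.1, and say how cycles are counted.
- For DFS, replace the cycle anchors with one imaging calendar counted from randomisation, identical in both arms and independent of the number of cycles given, running to an evaluation at month 36. The sponsor chooses the interval.
- In section 5.4, replace the reference in "imaging assessments should continue to be conducted at the frequency specified in this study" with a reference to that calendar, so that the censoring date in section 6.2(3) can reach three years and a missed scan can be recorded as a deviation.
- State whether the preoperative assessments include imaging.

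**Cost:** a short amendment, submitted to the ethics committee as section 13 requires, and some additional follow-up scans at sites that would have imaged less often. Section 5.4 already commits sites to continued imaging, so the change mainly dates an existing obligation. Sample size and the primary analysis do not change.

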5.3 End of treatment/exit from study visit

When the subject has completed the study treatment/exited the study, relevant assessments and examinations are required. They should be performed as follows:

- Weight and ECOG score;
- Life signs: pulse, respiratory rate, body temperature and blood pressure;
- Comprehensive physical examination: general condition, head and face, skin, lymph nodes, eyes, ear, nose and throat, oral cavity, respiratory system, cardiovascular system, abdomen, reproductive and urinary system, musculoskeletal, nervous system and mental state;
- Complete blood count: red blood cell count, hemoglobin, platelet count,

white blood cell count, neutrophil count and lymphocyte classification count;

- Routine urine: white blood cells, red blood cells, proteinuria; if proteinuria is greater than or equal to 2+, 24-hour urine protein quantification should be added;
- Blood biochemical: ALT, AST, γ -GT, TBIL, DBIL, AKP, BUN or urea (preferably BUN), TP, ALB, Cr, GLU, K+, Na+, Ca2+, Mg2+, Cl-;
- Tumor markers;
- Coagulation function: activated partial thromboplastin time (APTT), prothrombin time (PT), thrombin time (TT), fibrinogen (FIB), international normalized ratio (INR);
- 12. Lead electrocardiogram: attention should be paid to QT, QTc and P-R intervals. If there are abnormalities, other relevant tests should be done according to the investigator's judgment;
- Document adverse events.

5.4, follow-up period

The survival follow-up period ends when the subject dies, is lost to follow-up, withdraws from informed consent and refuses to continue providing information, or the sponsor terminates the study. During this period, a visit is conducted every three months through telephone or other effective methods to collect survival information and details about subsequent anti-tumor treatments (if the subject starts new anti-tumor treatment, the treatment plan and its duration should be recorded).

For subjects without imaging evidence of disease progression, imaging assessments should continue to be conducted at the frequency specified in this study until the subject experiences disease progression, death, loss to follow-up, withdrawal of informed consent and refusal to continue providing information, initiation of other anti-tumor treatments, or termination of the study by the sponsor. Every effort should be made to obtain imaging evidence of disease

progression in these subjects.

6. Effectiveness evaluation

6.1 Effectiveness parameters:

The main efficacy indicator of this study was the proportion of patients in each treatment group who achieved tumor downstaging (ypTNM 0-I stage), and the secondary efficacy indicators were the proportion of patients with complete pathological remission, 3-year disease-free survival (DFS), overall survival time (OS) and tumor regression grade TRG.

6.2 Evaluation criteria of effectiveness:

This study evaluated the proportion of patients with YWHAB high expression locally advanced rectal cancer who achieved tumor downstaging (ypTNM 0-I stage) in neoadjuvant treatment with mFOLFOX6 combined with citrus flavonoid tablets (Aimalang).

- (1) Downstaging rate of tumor (ypTNM 0-I stage): the proportion of patients with locally advanced rectal cancer who received mFOLFOX6 or mFOLFOX6 combined with citrus flavonoid tablets (Aimalang) as neoadjuvant chemotherapy, and the proportion of patients with postoperative pathological stage of ypTNM 0-I stage in surgical specimens.
- (2) The degree of pathological remission is defined as follows: ① Complete Remission (CR): All tumor target lesions have disappeared, no new lesions have appeared, and tumor markers are normal, lasting at least 4 weeks. ② Partial Response (PR): The sum of the maximum diameters of tumor target lesions has decreased by at least 30%, lasting at least 4 weeks. ③ Stable Disease (SD): The sum of the maximum diameters of tumor target lesions has not decreased by more than PR, or increased by less than PD. ④ Disease Progression (PD): The sum of the maximum diameters of tumor target lesions has increased by at least 20%, or new lesions have appeared.

Subjects who did not meet the primary endpoint criteria are included in the denominator but not in the numerator.

- (3) When determining the disease-free survival (DFS), clinical deterioration without clear evidence of disease progression according to the RECIST 1.1 criteria is not considered a disease progression. For subjects who died without prior reported disease progression, it is considered that the disease progressed at the time of death. Subjects who have neither experienced disease progression nor died will be censored at their last evaluable tumor evaluation date. Independent central imaging review will be conducted to confirm the independent central imaging service provider of the subject, which will receive all images from the research center and assess the subject's disease progression according to the RECIST 1.1 criteria.
- (4) Survival record and evaluation: the subject will be followed up every 3 months on disease and survival after the end of treatment or withdrawal from the group, by telephone follow-up, until death, loss to follow-up, withdrawal of informed consent and refusal to continue to provide information or termination of the study by the sponsor.
- (5) Tumor regression grading TRG: TRG 0 means no residual tumor cells, TRG 1 means a single cell or small group of cells; TRG 2 means residual cancer with a proliferative response to connective tissue; TRG 3 means minimal evidence of tumor response.

7. Safety evaluation

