8.3 Efficacy analysis and statistical methods

For the proportion of patients in each treatment group who achieved tumor downstaging (ypTNM 0-I stage), the proportion of participants with pathological complete remission, and the tumor regression grading (TRG), statistical analysis was conducted using mean values and standard deviations. For the three-year disease-free survival rate and overall survival time, Kaplan-Meier curves were plotted, and the 95% confidence interval for the median time was calculated using the Brookmeyer Crowley method. The Log-rank test was used to compare differences between groups, and the hazard ratios (HR) for each endpoint were

estimated using the Cox proportional hazards model, exploring the impact of factors other than treatment on these endpoints. Additionally, the number and percentage of cases that occurred at each endpoint, as well as the number and percentage of censored cases, were calculated and categorized by censoring reason.

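### Residual tumour at surgery is a DFS event in section 2.3(2), but the censoring sentence in section 6.2(3) recognises only progression and death

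*Combined protocol and SAP*

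**What the plan says.** Section 2.3, secondary endpoint (2), defines 3-year DFS from randomization by a list of events: "disease progression, surgical gross/microscopic tumor residue, local recurrence, distant metastasis, or death for any reason, whichever occurs first". Residue at surgery is a separate item from progression in that list.

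Section 6.2(3) sets out how DFS is to be determined. Clinical deterioration without clear RECIST 1.1 evidence does not count as progression, and an independent central review of images assesses progression. Deaths are covered: "For subjects who died without prior reported disease progression, it is considered that the disease progressed at the time of death". Everyone else is covered by one sentence: "Subjects who have neither experienced disease progression nor died will be censored at their last evaluable tumor evaluation date". Residue at surgery is not mentioned.

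Section 8.3 plans Kaplan-Meier curves, a log-rank test and a Cox model for DFS. It also asks for the number of events at each endpoint, and says that "the number and percentage of censored cases, were calculated and categorized by censoring reason". It adds no event or censoring rule of its own.

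**The concern.** The two sections classify the same patient differently. Residue is known at or soon after surgery, often well before any RECIST progression. Microscopic residue is a pathology finding that a central review of images would not be expected to detect. An analyst who programs DFS from 2.3(2) counts these patients as events. One who programs it from 6.2(3) as worded keeps them at risk and censors them unless progression or death is recorded later.

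Three-year DFS is a named secondary efficacy endpoint in an open-label trial. Two competent analysts could report different event counts, censoring counts and 3-year rates from the same data, and a choice made after the data are seen would be hard to defend.

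**Working it through.** **Comparing the rules.** The documents state no DFS rate, hazard ratio or residue rate, so there is no planned figure to reproduce. The core of the check is textual.

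| Patient | Section 2.3(2) | Section 6.2(3) as worded |
|---|---|---|
| Residue, no later progression or death | Event | Censored at last evaluable tumour assessment |
| Residue, then RECIST progression or death | Event because of the residue | Event, dated at progression or death |
| No residue, RECIST progression or death | Event | Event, same date |

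No other section reconciles them. Section 7.4, in the safety chapter, describes progression without including surgical residue. Section 5.4 deals with follow-up imaging, and 8.3 only tabulates.

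**Size, with assumed inputs.** Let r be the share of patients with residue, e the share of those with no RECIST progression or death by 3 years, and S0 the 3-year DFS in everyone else. With all patients followed to year 3:

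- under 2.3(2): DFS = (1 - r) × S0
- under 6.2(3): DFS = (1 - r) × S0 + r × e
- difference: r × e, whatever S0 is

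Take r = 5%, e = 30-60% and N = 236 (section 8.5), with all 236 assumed to have surgery:

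- patients with residue: 236 × 0.05 = 11.8
- classified differently: 11.8 × 0.30 = 3.5 to 11.8 × 0.60 = 7.1
- events under both rules but dated differently: 11.8 × 0.40 = 4.7 to 11.8 × 0.70 = 8.3
- gap in 3-year DFS: 0.05 × 0.30 = 1.5 points to 0.05 × 0.60 = 3.0 points

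Over r = 2-10%, with e still 30-60%, the gap runs from 0.02 × 0.30 = 0.6 to 0.10 × 0.60 = 6.0 points.

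**Simulation.** The formula ignores scan timing and censoring, so the Kaplan-Meier estimate was also simulated. The assumptions, none of them from the documents, were: 800 replicates, 106 operated patients per arm, surgery at month 4, scans every 3 months, data cut-off at months 48-72, control 3-year DFS of 75% without residue, a hazard ratio of 0.75 for progression or death, and 5% residue in both arms.

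| e | Gap in 3-year DFS | Mean date shift* | HR under 6.2(3) | HR under 2.3(2) |
|---|---|---|---|---|
| 30% | 1.8 points | 14.8 months | 0.768 | 0.787 |
| 60% | 3.3 points | 16.1 months | 0.753 | 0.784 |

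*Among residue patients with an event by month 36, taking residue as an event at surgery.

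A repeat run gave gaps of 2.0 and 3.3 points. Formula and simulation together span about 1.5 to 3.3 points at 5% residue.

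**Separate check on the imaging line.** Section 5.2 says: "Imaging evaluation was performed after 6 cycles and 12 cycles of mFOLFOX6 regimen adjuvant chemotherapy". Section 4.1 says: "The mFOLFOX6 regimen involves 4-6 cycles before surgery and 6-8 cycles after surgery". If adjuvant means after surgery, 12 cycles are never reached, because the maximum is 8. If 12 is a total, the permitted schedules 4+6 = 10, 4+7 = 11 and 5+6 = 11 fall short, while 6+6 = 12 reaches it.

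**The case against.** The strongest reply is that 2.3(2) is the definition and 6.2(3) only explains how progression is judged. On this view, progression in 6.2(3) is shorthand for any DFS event. That paragraph also leaves out local recurrence and distant metastasis, and it already treats death as progression, so the word is being used loosely. The document also reads as a translation, which argues against putting much weight on one omission.

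This reading is possible, and it may be what the authors meant. The text does not say so. 2.3(2) separates residue from progression, 6.2(3) ties progression to RECIST and images, and its censoring sentence has no exception. Recurrence and metastasis would normally appear on imaging as new lesions; microscopic residue would not. If shorthand was intended, the same one-sentence change records it.

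Two further objections stand. The size rests wholly on assumed inputs. And no section lists resection margin or residue status as a collected item; the documents call for ypTNM stage and regression grade. A reader might infer that the correction needs no new data because the pathology report will hold the answer. That is plausible, but the documents do not establish it, least of all for gross residue.

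A reader might also infer that the treatment comparison is biased. The documents do not support that. With equal residue in both arms, the simulated hazard ratio hardly moved. With an assumed 8% residue in control and 3% in the experimental arm, it went from about 0.74 under 6.2(3) to 0.69 under 2.3(2) at 60% event-free, and from 0.69 to 0.68 at 30%. Nothing in the documents says whether residue will differ by arm, or in which direction.

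The cycle count in 5.2 is a separate matter. On the total-cycles reading it fits section 4.1's own reference to six planned cycles before surgery: "If a patient cannot tolerate the planned 6 cycles of neoadjuvant therapy, early surgery can be considered". It lends no weight to the DFS point.

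**Conclusion.** The point holds. As worded, 6.2(3) yields a 3-year DFS that departs from the protocol's own definition in 2.3(2). It should be corrected before analysis. The consequence is limited to one secondary endpoint and the 8.3 event and censoring tables; the primary downstaging endpoint is not touched, and no material effect on the hazard ratio is claimed.

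The gap is roughly the residue share times the share of those patients otherwise event-free at 3 years: about 1.5 to 3.3 points at an assumed 5% and 30-60%. It would be smaller if residue is rare or if nearly all such patients progress within 3 years, in which case mainly the event dates differ. The formula also assumes imaging to year 3. Section 5.4 lets protocol imaging stop when other anti-tumour treatment starts, so some residue patients could be censored early under 6.2(3) and never have progression recorded.

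**What to change.** - In 6.2(3), refer to the 2.3(2) list as the only DFS event definition.
- Count gross or microscopic residue at surgery as an event with a stated date, for example the date of surgery; 2.3(2) gives none.
- Censor at the last evaluable tumour assessment only those patients with none of the 2.3(2) events.
- Keep RECIST 1.1 with central review as the rule for the progression component.
- Confirm that the CRF records residue status, including gross residue. If it does not, an item must be added.

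The cost is a short wording change submitted to the ethics committee under section 13, plus possibly one CRF item. The downside is a slightly lower reported 3-year DFS, by the gap given above.

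As a separate, minor clarification, reconcile the imaging line in 5.2 with the cycle ranges in 4.1. Also say what 5.4 refers to when it states that "imaging assessments should continue to be conducted at the frequency specified in this study": no follow-up scan interval is given, and the three-monthly contacts there are by telephone or other means.
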